⁹ PD (MIC-1 only) and PK: Day 3 (Day 3 for DEP only): Collect blood samples 48 hours (± 4 h) after the initiation of Day 1 infusion. Day 4: Collect blood samples within 1 hour prior to SOI. Visit to be completed in EXP only if biopsy performed. In EXP, PK and PD not collected at this visit.

¹⁰ In patients consenting to optional biopsies, buccal swab for germline DNA (EXP only)

¹¹ RECIST 1.1 - (for solid tumor patients) or IWG 2014- (for lymphoma patients) compliant imaging for disease assessment and tumor measurements as well as laboratory-based assays (e.g., prostate specific antigen) for patients with relevant disease indications.

¹² During the first two cycles, ALRN-6924 should be administered in the morning to allow observation of delayed infusion reactions. ALRN-6924 will be infused over 1 hour (± 15 min). At the end of the infusion, IV fluids (saline) or oral fluids (500mL – 1000 mL) should be administered unless clinically contraindicated.

¹³ All concomitant medications taken within 28 days of beginning the study (Cycle 1 Day 1) until 30 days after last infusion or start of subsequent therapy must be reported in the relevant eCRF pages, including supportive care drugs and drugs used for treatment of AEs or chronic diseases.

¹⁴ AE reporting begins at the point of the first ALRN-6924 infusion and continues until 30 days after last infusion or start of subsequent therapy; until all drug-related toxicities and ongoing SAEs have resolved, whichever is later; or until the Investigator assesses AEs as “chronic” or “stable.”

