possibly, probably or definitely attributed to ALRN-6924. Grading of AEs will be defined by the NCI Common Terminology Criteria for Adverse Events (CTCAE) version 4.03 (See [Appendix O](#)). As drug-related AEs Grade ≥ 2 occurred in DL-4A (fatigue) and in DL-3B (neutropenia), subsequent dose escalations with DL-5A and DL-4B continued using modified Fibonacci sequence (i.e., 67%, 50%, 40%, and 33%).

Escalation to the next dose level within each DR may proceed in the absence of DLT at the completion of Cycle 1 (treatment cycle = 28 days for DR-A, DR-A-2 and 21 days for DR-B). Escalation to the next dose level within each DR as well as the DR and DL for the EXP cohorts will be decided by a Safety Review Committee (SRC), consisting of the Principal Investigators and Sponsor's Medical Monitor, which will review all available safety information from all patients. As two DLTs have occurred in DR-7A (hypotension and hepatobiliary laboratory abnormalities), there will be no further escalation in DR-A. A new modified infusion regimen was tested (DR-A-2) starting at DR-7A-2. As two DLTs have occurred in DR-7A-2 (anemia and neutropenia), there will be no further escalation in DR-A-2.

Based on review of available safety and PK data during this and other studies with ALRN-6924, dose escalation or modification steps may be adjusted (i.e. increased or decreased) by the SRC to limit the number of patients exposed to sub-therapeutic dose levels as well as to ensure patients' safety.

Within each Dose Regimen cohort:

- If no DLT is observed in a cohort, the subsequent patient group will be enrolled at the next planned dose level of that dose regimen.
- If a DLT is observed in ≥ 2 of 3 patients at any dose level, no further dose escalation will occur in that DR, and the current dose will be defined as the maximum administered dose (MAD).

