5.6 Dose Escalation Criteria (DEP)

In the absence of >33% of patients experiencing a drug-related DLT, escalation to the next dose level for a given treatment arm may proceed when all of the following have occurred:

- At the completion of Cycle 1 (treatment cycle = 28 days for DR-A and DR-A-2 or treatment cycle = 21 days for DR-B),
- The Safety Review Meeting is convened during which the Safety Review Committee (SRC), consisting of the Investigators and Sponsor's Medical Monitor, has reviewed all available safety data for all patients in the cohort and confirms that the next planned dose level is appropriate; and
- The Sponsor Medical Monitor issues written documentation of the decision to proceed to the next planned dose level of a dose regimen.

It is important to note that despite the absence of >33% of patients experiencing a DLT, the next dose level may be less than the planned dose level if the Investigators and Sponsor's Medical Monitor agree that a more conservative dose escalation approach is warranted or would be in the best interest of the patients. The SRC may hold the dose (e.g., stop dose escalation) at their discretion and enroll additional patients until sufficient safety data are obtained to determine escalation of the current dose level or to confirm a certain dose as an MTD or OBD.

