5.7.1 Dose Levels for the Dose Escalation Portion of the Study

In the Dose Escalation portion of the study, increasing dose levels of ALRN-6924 will be evaluated in cohorts of 3-6 DLT-evaluable patients per dose regimen. Patients enrolled in Cohort 1 receive ALRN-6924 at Dose Level 1 (0.16 mg/kg). Based on allometric scaling, at 0.16 mg/kg dose in humans, the predicted AUC (50 $\mu\text{g}\cdot\text{hr}/\text{mL}$) is approximately 9% of the rat AUC at STD_{10} and approximately 6% of the AUC at the monkey HNSTD as described in Section 1.4.

In the absence of DLT in >33% of DLT-evaluable patients in either DR, subsequent cohorts of 3 to 6 patients will receive escalated doses until the MTD or an OBD is established for each dose regimen.

A 2-stage dose escalation design will be employed. During the initial Stage 1 Escalation Phase, 100% dose increments will be utilized until ≥ 1 of 3 patients in a cohort experiences any Grade ≥ 2 AE that is at least possibly related to study drug. Study drug-related AEs Grade ≥ 2 occurred in DL-4A (fatigue) and in DL-3B (neutropenia). Therefore, per protocol, Stage 2 has been implemented for subsequent dose escalations starting with DL-5A and DL-4B. Dose escalation will continue using 3-patient cohorts and the modified Fibonacci sequence (i.e., 67%, 50%, 40%, 33%), until the MTD or an OBD is established. As two DLTs have occurred in DR-7A (hypotension and hepatobiliary laboratory abnormalities), there will be no further dose escalation in DR-A. A new modified infusion regimen was tested (DR-A-2) starting at dose level 7A-2 (=4.4 mg/kg body-weight). As two DLTs have occurred in DR-7A-2 (anemia and neutropenia), there will be no further escalation in DR-A-2.

Figure 9: Dose Level and Dose Regimen Schematic

The observation of DLT(s) will be used to make individual patient determinations regarding dose reductions, interruptions or discontinuation throughout the course of the trial, but DLTs occurring during Cycle 1 will be used to inform safety and tolerability assessments for dose escalation decisions.

If DLTs are observed in the first cohort, the dose will be de-escalated to Dose Level -1. If DLTs are observed at Dose Level -1, the dose will be de-escalated to Dose Level -2. If DLTs are observed at Dose Level -2, other dose levels may be considered and implemented after discussions among the Investigators and Sponsor's Medical Monitor.

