5.9.2 Definition of Dose-Limiting Toxicity

A DLT will be defined as any Grade ≥ 3 AE that is considered to be possibly, probably, or definitely related to the study drug, with the following exceptions: (1) for fatigue, nausea, emesis, diarrhea or mucositis, only Grade ≥ 3 AE that do not respond within 48 hours to standard supportive/pharmacological treatment will be considered DLT; (2) for electrolyte imbalances, only Grade ≥ 3 AE that do not respond to correction within 24 hours will be considered DLT; (3) for infusion reactions, only a Grade 3 reaction which caused hospitalization or Grade 4 will be considered a DLT. In addition, specific hematologic DLTs are defined as:

- Thrombocytopenia – Grade 4 of any duration, Grade 3 for ≥ 7 days, or Grade 3 associated with clinically significant bleeding
- Neutropenia – Grade 4 for ≥ 3 days, or any Grade ≥ 3 febrile neutropenia

The above criteria will be used to make individual patient determinations regarding dose reductions, interruptions or discontinuation throughout the course of the trial, but DLTs occurring during Cycle 1 will be used to inform safety and tolerability assessments for dose escalation decisions.

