6.9 Laboratory Assessments

Laboratory assessments to be performed locally may include:

- Clinical chemistry (glucose, calcium, albumin, total protein, sodium, potassium, CO₂, chloride, phosphate, BUN [blood urea nitrogen], serum creatinine, uric acid, alkaline phosphatase, ALT, AST, LDH, total and direct bilirubin).
- Hematology (complete blood count, platelets and differential).
- Urinalysis (dipstick measurement [pH, specific gravity, protein, glucose, ketones, nitrite, leukocyte esterase] with microscopic analysis, if results of the dipstick indicate additional testing required).
- Coagulation (PT, INR, aPTT).
- Serum or urine pregnancy test (Beta human chorionic gonadotropin [β -hCG]) for women of child-bearing potential.

- At select visits, lymphocyte subset testing will be performed (B-cells, T-cells including CD4 and CD8, natural killer [NK] cells).
- C-reactive protein, fibrinogen, and reticulocytes will also be collected at select visits.
- HPV testing of tumor tissue from cancers likely to be HPV-positive: to be performed dependent upon cancer type, including (but not limited to) cervical cancer, oropharyngeal cancer, head and neck squamous cell cancers or anal cancer.
- HIV, Hepatitis B and C testing

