APPENDIX C: Dose Regimen A and A-2 - Study Activities Through Cycle 1 - ALRN single agent therapy

	Molecular Screen	Clinical Screen -21 days	Within 7 days prior to Day 1	Day 1		Day 2	Day 3 DEP only	Day 8 EXP: ± 1 d		Day 15 EXP: ± 1 d		Day 16	Day 22 ¹⁵ ±1 d
				Pre-Dose	Post-Dose			Pre-Dose	Post-Dose	Pre-Dose	Post-Dose		
Written informed consent	See 6.2	See 6.2											
Medical and disease history		X											
Demographics		X											
Tumor biopsy or archive tissue sample	See 3.2 ¹												
Eligibility		X	X										
Blood test for HIV, hepatitis B and C		X											
HPV test ³		X											
Serum or urine pregnancy test			Within 2 days prior to Day 1										
Vital signs ⁴		X	X	X	X	X	X	X	X	X	X	X	X
Physical exam ⁵		X		X				X		X			
12-lead ECG ⁶		X		X	X								
Laboratory assessments – chemistry		X	X ²	X		X	X	X		X		X	
Laboratory assessments – hematology		X	X ²	X		X	X	X		X		X	X
Laboratory assessments - coagulation		X	X ²	X		X	X	X		X		X	
Laboratory assessments - urinalysis		X	X ²	X		X	X	X		X		X	
Laboratory assessments – lymphocyte subset testing			X			X		X					
Laboratory assessments – CRP, fibrinogen			X	X		X	X	X		X		X	
Laboratory assessments – reticulocytes				X									
Blood Collection – immunogenicity					X ⁷								
Blood Collection - PD assessments-MIC-1					X ⁷	X ⁷	X ⁸	X ⁹					
Blood Collection - PD assessments-CTC DEP and select sites in EXP					X ⁷	X ⁷	X ⁸						
Blood Collection - PK assessments					X ⁷	X ⁷	X ⁸	X ⁹					
Blood Collection –cell-free DNA	X												

	Molecular Screen	Clinical Screen -21 days	Within 7 days prior to Day 1	Day 1		Day 2	Day 3 DEP only	Day 8 EXP: ± 1 d		Day 15 EXP: ± 1 d		Day 16	Day 22 ¹⁵ ±1 d
Germline DNA sample ¹⁰				X									
ECOG Performance Status		X	X					X		X			
Biopsy for biomarker assessments /p53 status												X ¹	
Tumor Assessment/Imaging ¹¹		X											
ALRN-6924 dosing ¹²				X				X		X			
Concomitant medications ¹³		X	X	X	X	X	X	X	X	X	X	X	X
AE assessment ¹⁴					X	X	X	X	X	X	X	X	X

DEP: For Days 1 through 16, no pre-specified visit windows exist to ensure timely safety follow-up and PK/PD sampling. However, at the Investigator's discretion, it may be necessary to conduct a study visit on an alternative day than described in this schedule in order to protect the safety, rights, or welfare of the patient. If this is the situation, the Investigator will confer with and obtain approval from the Medical Monitor.

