Tumor biopsy or archive tissue sample	See 3.2 ¹													
Eligibility		X	X											
Blood test for HIV, hepatitis B and C		X												
HPV test ³		X												
Serum or urine pregnancy test			Within 2 days prior to Day 1											
Vital signs ⁴		X	X	X	X	X	X	X	X	X	X	X	X	X
Physical exam ⁵		X		X				X		X				
12-lead ECG ⁶		X		X	X									
Laboratory assessments – chemistry		X	X ²	X		X	X	X		X		X	X	
Laboratory assessments – hematology		X	X ²	X		X	X	X		X		X	X	X
Laboratory assessments - coagulation		X	X ²	X		X	X	X		X		X	X	
Laboratory assessments - urinalysis		X	X ²	X		X	X	X		X		X	X	
Laboratory assessments – lymphocyte subset testing			X			X		X						
Laboratory assessments – CRP, fibrinogen			X	X		X	X	X		X		X	X	
Laboratory assessments – reticulocytes				X										
Blood Collection - immunogenicity				X ⁷										
Blood Collection - PD assessments-MIC-1				X ⁷	X ⁷	X ⁸	X ⁹	X ⁹						
Blood Collection - PD assessments-CTC DEP and select sites in EXP				X ⁷	X ⁷	X ⁸								
Blood Collection - PK assessments				X ⁷	X ⁷	X ⁸	X ⁹	X ⁹						

	Molecular Screen	Clinical Screen -21 days	Within 7 days prior to Day 1	Day 1		Day 2	Day 3 ⁹	Days 4 and 8 EXP: ± 1 d	Day 11 EXP: ± 1 d	Day 12 DEP only	Day 15 ± 1 d EXP only	Day 18 ± 1 d DEP only
Blood Collection – cell-free DNA	X											
Germline DNA sample ¹⁰				X								
ECOG Performance Status		X	X					X	X			
Biopsy for biomarker assessments/p53 status							EXP: Day 3 or 10 ¹			DEP: X ¹		
Tumor Assessment/Imaging ¹¹		X										
ALRN-6924 dosing ¹²				X				X	X			
Concomitant medications ¹³		X	X	X	X	X	X	X	X	X	X	X
AE assessment ¹⁴				X	X	X	X	X	X	X	X	X

DEP: For Days 1 through 12, no pre-specified visit windows exist to ensure timely safety follow-up and PK/PD sampling. However, at the Investigator's discretion, it may be necessary to conduct a study visit on an alternative day than described in this schedule in order to protect the safety, rights, or welfare of the patient. If this is the situation, the Investigator will confer with and obtain approval from the Medical Monitor.

¹ A pre-treatment biopsy or archival sample is required for p53 testing. For patients with a study biopsy performed immediately prior to enrollment, optional needle biopsy to be performed within 24 (DEP) or 48 (EXP) hours of Cycle 1 Day 11 infusion OR Cycle 2 Day 11 infusion. In EXP, optional biopsies include pre-treatment, during treatment, and one or more at times of suspected and/or confirmed progression.

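### In dose escalation no chemistry is scheduled between Day 16 (DR-A/A-2) or Day 12 (DR-B) and the Cycle 2 pre-dose draw, leaving 32–43% or 29–43% of the DLT window untested

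*Protocol*

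**What the plan says.** Protocol Section 5.9.2 fixes the window for dose decisions: "DLTs occurring during Cycle 1 will be used to inform safety and tolerability assessments for dose escalation decisions". Section 5.6 gives its length: "treatment cycle = 28 days for DR-A and DR-A-2 or treatment cycle = 21 days for DR-B". The chemistry panel in Section 6.9 covers electrolytes and liver tests; its list ends "uric acid, alkaline phosphatase, ALT, AST, LDH, total and direct bilirubin".

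- **Appendix C (DR-A and DR-A-2, Cycle 1).** The row "Laboratory assessments – chemistry" is marked on Days 1, 2, 3, 8, 15 and 16 and is blank on Day 22. The row "Laboratory assessments – hematology" is marked on the same days and also on Day 22. Note 15 makes the Day 22 visit apply to every escalation patient.
- **Appendix E (DR-B, Cycle 1).** The column "Day 18 ± 1 d DEP only" has the same pattern: hematology marked, chemistry blank. Chemistry on Day 15 is for expansion patients only, so the escalation draws are Days 1, 2, 3, 4, 8, 11 and 12.
- **Appendices D and F (Cycle 2 onward).** The next chemistry is pre-dose on Cycle 2 Day 1. Note 1 in each lets this work be done up to 3 days before that dose, and it concerns patients who continue treatment.

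Section 5.7.1 records the relevant history: "As two DLTs have occurred in DR-7A (hypotension and hepatobiliary laboratory abnormalities), there will be no further dose escalation in DR-A". The same section says that escalation in DR-A-2 has also stopped.

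**The concern.** The DLT window is the whole of Cycle 1, but scheduled chemistry stops about a day after the last infusion of the cycle. The one remaining visit in the window takes blood and does not use it for chemistry.

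A related Grade 3 or higher liver abnormality in Cycle 1 can be a DLT, and a hepatobiliary laboratory DLT has already occurred in this trial. Such an abnormality may cause no symptoms, so it may be found only by a scheduled test. In a 3+3 design one event can change the decision. Section 5.7.2 reports one DLT in six evaluable patients at DL-6A, and Section 5.9.3 allows at most one in six at the MTD. An event that rises and resolves between draws would not enter that count. The SAP cannot recover it: Section 3.3 imputes no missing safety results, and Section 8.2 only tabulates the DLTs reported.

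**Working it through.** The plan states no figure for this coverage, so there is none to reproduce.

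**Inputs.** Cycle length is 28 days (DR-A/A-2) or 21 days (DR-B), from Section 5.6. The last Cycle 1 chemistry is Day 16 (Appendix C) or Day 12 (Appendix E, escalation). The Cycle 2 Day 1 pre-dose draw is 0 to 3 days before that dose (Appendices D and F). I take Cycle 2 to start on schedule, on Day 29 or Day 22; the column header also carries a ±3 day window, which could widen the ranges.

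**Pre-dose draw window.** From (cycle length + 1 − 3) to (cycle length + 1): Days 26–29 for DR-A/A-2 and Days 19–22 for DR-B.

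**Untested share of the DLT window** = untested days after the last Cycle 1 chemistry / cycle length.

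- DR-A/A-2, latest pre-dose draw: Days 17–28, (28 − 16)/28 = 12/28 = 42.9%.
- DR-A/A-2, earliest: Days 17–25, (25 − 16)/28 = 9/28 = 32.1%.
- DR-B, latest: Days 13–21, (21 − 12)/21 = 9/21 = 42.9%.
- DR-B, earliest: Days 13–18, (18 − 12)/21 = 6/21 = 28.6%.

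The interval between draws is 26 − 16 = 10 to 29 − 16 = 13 days (DR-A/A-2), or 19 − 12 = 7 to 22 − 12 = 10 days (DR-B).

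**Patients who do not start Cycle 2.** The End of Treatment visit is 30 ± 5 days after the last dose (Section 6.13), or at study withdrawal. After a full Cycle 1 the timed visit falls on Days 15 + 25 = 40 to 15 + 35 = 50 (DR-A/A-2) or 11 + 25 = 36 to 11 + 35 = 46 (DR-B). Both lie beyond the window; only an earlier withdrawal visit could fall inside it.

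**Detection.** Assume onset is equally likely on each of Days 17–28 (12 days) or Days 13–21 (9 days). An event lasting L days is seen if a draw falls between onset and onset + L − 1. A pre-dose draw on Day 29 or 22 is credited to Cycle 1 if onset was in Cycle 1. The cells list the onset days that are caught, with the added draw on its nominal day.

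| Regimen, pre-dose draw | Schedule | L = 5 | L = 7 |
|---|---|---|---|
| DR-A/A-2, Day 29 | current | 25–28: 4/12 = 33% | 23–28: 6/12 = 50% |
| | plus Day 22 | 18–22, 25–28: 9/12 = 75% | 17–28: 12/12 = 100% |
| DR-A/A-2, Day 26 | current | 22–26: 5/12 = 42% | 20–26: 7/12 = 58% |
| | plus Day 22 | 18–26: 9/12 = 75% | 17–26: 10/12 = 83% |
| DR-B, Day 22 | current | 18–21: 4/9 = 44% | 16–21: 6/9 = 67% |
| | plus Day 18 | 14–21: 8/9 = 89% | 13–21: 9/9 = 100% |
| DR-B, Day 19 | current | 15–19: 5/9 = 56% | 13–19: 7/9 = 78% |
| | plus Day 18 | 14–19: 6/9 = 67% | 13–19: 7/9 = 78% |

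The rows are the two ends of the pre-dose window. In between, the 75% for DR-A/A-2 becomes 10/12 = 83% (pre-dose draw on Day 27 or 28, with Day 22); the other in-between results stay within the ranges shown.

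**Tail after the change, with the latest pre-dose draw.** Days 23–28, 6/28 = 21.4% (DR-A/A-2); Days 19–21, 3/21 = 14.3% (DR-B).

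**The case against.** Several points on the other side stand.

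- **The pre-dose draw.** A reader of the Cycle 1 tables alone might infer that the last 43% of the window has no liver or electrolyte tests. That goes too far: the Cycle 2 pre-dose chemistry can fall inside the window, and unscheduled tests are allowed. An abnormality that persists would be found in a patient who continues.
- **The DLT filters.** A laboratory value is an adverse event only if the investigator judges it clinically significant, it needs intervention, or it alters dosing (Sections 8.1.1 and 8.3). An electrolyte event is a DLT only if it fails to respond to correction within 24 hours (Section 5.9.2), so one that settles unseen and untreated would often not qualify. The point therefore rests mainly on liver tests.
- **Comparison with other cohorts.** Because DR-B expansion draws chemistry on Day 15 and the combination cohort on Day 22, a reader might infer that escalation is followed less closely overall. The tables do not support this. DR-B escalation has seven Cycle 1 chemistry days against six in DR-B expansion (Days 1, 2, 4, 8, 11, 15), and DR-A escalation has six against five in the combination cohort (Days 1, 2, 8, 15, 22). The combination run-in is also judged with the DLT definition as a guide (Section 5.7.2), and palbociclib runs to Day 21, which may explain a Day 22 draw. What differs is the timing of the draw after the last infusion.
- **A rationale for hematology only.** The animal DLT was marrow suppression, with chemistry changes judged secondary (Section 1.4.2).

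The other safeguards do not close the gap. The provision for repeat tests in Section 5.8.1 follows an adverse event already observed. The re-evaluation in Section 5.9.3 needs a later toxicity to be seen. Tumor lysis tests in Cycle 1 precede each infusion (Section 5.4.1.3). Replacement under Section 4.8 covers patients who leave or miss doses in Cycle 1 for non-safety reasons, not those who complete it and stop.

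**Conclusion.** The point holds as a gap in scheduled ascertainment: 32–43% (DR-A/A-2) or 29–43% (DR-B) of the DLT window for continuing patients, and possibly the whole remainder of the window for a patient who completes Cycle 1 dosing but does not start Cycle 2. A transient, symptom-free Grade 3 or higher liver abnormality in that stretch could be missed.

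The detection gains rest on uniform onset and on assumed durations of 5 and 7 days, neither of which the documents give. The gain is clear for DR-A/A-2. For DR-B it depends on when the pre-dose draw is taken, and a 7-day event gains nothing if that draw is on Day 19.

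A reader might infer that a DLT was missed, or that the recommended dose was set too high. The documents show neither. The hepatobiliary DLT was detected, and its cycle day is not stated, so it does not show that such events fall in the gap. The forward effect is also limited: escalation in DR-A and DR-A-2 has stopped, which leaves DR-B escalation, for which no stop is stated, and any patients added to explore the MTD or OBD (Section 5.7.1). This is a cheap improvement to DLT ascertainment, not a flaw that undermines the design.

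**What to change.** In Appendix C, mark chemistry in the Day 22 column for escalation patients. In Appendix E, mark chemistry in the Day 18 column, which is already for escalation patients only. Both use the blood draw already taken for hematology.

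The cost is two table cells and one extra local chemistry panel per escalation patient, with no new visit and no new venipuncture. If the sponsor prefers to keep these visits to hematology only, the protocol should state the reason.

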- Levels of biomarkers (e.g., p53, MDM2, and MDMX gene sequence and copy number, as well as p21 RNA and/or protein expression) in tumor biopsy samples, and in blood, CTCs, where detectable, or MNC samples
- Incidence of anti-ALRN-6924 antibodies

Study Endpoints – Phase 2a dose expansion in MDM2 amplified or MDM2/CDK4 co-amplified solid tumors (ALRN-6924 plus palbociclib)

Primary endpoints:

- The proportion of efficacy-evaluable patients who achieve complete response (CR) or partial response (PR), per investigator assessment, in accordance with RECIST 1.1 or iRECIST (for solid tumor patients) or Response Assessment in Neuro-Oncology (RANO) criteria (for glioblastoma patients).
- Safety and tolerability including the occurrence of adverse events (AEs) and serious adverse events (SAEs), and changes from baseline in vital signs, laboratory analytes, and physical examination findings

Secondary endpoints:

- PK parameters, including AUC, C_{max} , T_{max} , and $t_{1/2}$ for ALRN-6924, its metabolites, and palbociclib
- The median time, in months, from the first response of CR or PR to disease progression or death from any cause (DOR)
- The median time, in months, for each of the following:
 - The first dose of ALRN-6924 to the first response of CR or PR (TTR)
 - The first dose of ALRN-6924 to disease progression or death from any cause (measured at 1 year and beyond) (PFS)
 - The first dose of ALRN-6924 to death from any cause (measured at 1 year and beyond) (OS)

Exploratory endpoint:

- The correlation of response with MDM2, MDMX, and/or CDK4 gene copy number and other genetic and protein biomarkers

Study Design

This is a Phase 1/2a open-label, multi-center, dose-escalation and dose expansion study designed to evaluate the safety, tolerability, PK, PD, and anti-tumor effects of ALRN-6924 administered by IV infusion using up to 4 different dosing regimens of a 28- or 21-day cycle (alone or in combination), in patients with advanced solid tumors or lymphomas with WT TP53 (see p53 Status Determination below). In Phase 1 and Phase 2a, patients will receive ALRN-6924 either once weekly for three consecutive weeks for a 28-day cycle (1 and 2 hour infusions may be tested) or twice weekly for two consecutive weeks for a 21-day cycle. In Phase 2a, dosing three times a week for one week over a 21-day cycle will be tested.

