The above criteria will be used to make individual patient determinations regarding dose reductions, interruptions or discontinuation throughout the course of the trial, but DLTs occurring during Cycle 1 will be used to inform safety and tolerability assessments for dose escalation decisions.

Study Drug Administration

ALRN-6924 will be administered as an IV infusion as follows:

Phase 1 Dose Escalation (ALRN-6924 administered as single agent therapy):

- Dose Levels 1 and 2 Dose Regimen A on Days 1, 8, and 15 of each 28-day cycle (1 hour infusion)
- Dose Levels 3 and beyond as follows –
 - Dose Regimen A on Days 1, 8, and 15 in a 28-day cycle (1 hour infusion)

- Dose Regimen B on Days 1 and 4, 8 and 11 in a 21-day cycle (1 hour infusion)
- Dose Regimen A-2 on Days 1, 8, and 15 in a 28-day cycle (2 hour infusion) [starting with Dose Level 7]

Patients who remain on study treatment for 2 years or longer may have their dosing frequency reduced, at the discretion of the investigator (i.e., Days 1 and 15 of a 28-day cycle (DR-A) or Days 1 and 8 of a 21-day cycle (DR-B). In the event that disease control is not maintained, the original dosing schedule may be resumed.

Phase 2a Dose Expansion in PTCL (ALRN-6924 administered as single agent therapy):

- Dose Regimen A 3.1 mg/kg on Days 1, 8, and 15 in a 28-day cycle (1 hour infusion)
- Dose Regimen B 2.7 mg/kg on Days 1 and 4, 8 and 11 in a 21-day cycle (1 hour infusion)
- Dose Regimen C 3.1 mg/kg on Days 1, 3 and 5 in a 21-day cycle (1 hour infusion). [If 3.1 mg/kg is not well tolerated, lower doses may be tested starting at dose levels of -25%]

Phase 2a Dose Expansion in MDM2 amplified or MDM2/CDK4 co-amplified solid tumors (ALRN-6924 plus palbociclib):

- ALRN-6924: 3.1 mg/kg (1 hour infusion) on Days 1, 8, and 15 in a 28-day cycle plus palbociclib: 100 mg per day orally on Days 1-21 in the same 28-day cycle. It is recommended that palbociclib be administered with food. On days when both drugs are administered (Days 1, 8, and 15 of each cycle), palbociclib should be administered at least 6 hours after the infusion of ALRN-6924.

Following the administration of each dose of ALRN-6924, patients must receive 500 to 1000 mL of IV or oral fluids, unless clinically contraindicated.

Statistical Methods

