7.5 Pharmacodynamic Analysis

Levels of p53, MDM2, MDMX, p21 and caspase will be measured in tumor specimens collected before beginning treatment, during Cycle 1 or Cycle 2 and at suspected disease progression. MIC-1 and CTCs will be measured in blood samples. Pharmacodynamic effects on the composition of cell free DNA from blood will be evaluated. Pharmacodynamic data will be tabulated and summarized by individual patient and collectively by dose level. Graphical displays will be provided where useful in the interpretation of results.

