³ Full physical examination to be performed at End of Treatment; all other physical examinations may be symptom directed. For patients on > 1 year, this procedure is no longer a mandatory study procedure. Weight to be collected at Day 1 (+/- 3 days) of each cycle.

⁴ ECGs to be performed after the patient has been supine for at least 10 minutes. Readings should be performed with the patient in the same physical position. Screening and pre-dose ECG recording should be taken in triplicate with 5-10 minutes between readings. Thereafter, subsequent readings on that same day will be performed in triplicate only if patient has a QTc that is a) >500 msec; b) increased by 60 msec over pre-dose; or c) decreased by 50 msec below pre-dose value. Timepoints on Day 22 of prior cycle or Day 1 of new cycle: At pre-dose (within 30 minutes prior to infusion) and EOI (+5 min). For patients on > 1 year, this procedure is no longer a mandatory study procedure.

⁵ For patients on > 1 year, the required labs are: full labs to be collected on Day 1, and hematology only at Day 11

⁶ Within 1 hour before SOI

⁷ PK (Cycle 2 only): Day 11 collect at EOI (+5 min) and at 1 hour (±5 min) and 4 hours (±10 min) after the end of infusion.

DEP only: PK (Cycle 2 only): Day 12 visit should be conducted and blood should be collected 24 hours (±4 h) after the initiation of Day 11 infusion.

⁸ For patients on > 1 year, this procedure is no longer a mandatory study procedure.

⁹ Cycle 2 biopsy not performed if collected in specified timepoint in Cycle 1. For patients with a study biopsy performed immediately prior to enrollment, optional needle biopsy to be performed within 24 hours (DEP) or 48 hours (EXP) of Cycle 1 Day 11 infusion OR Cycle 2 Day 11 infusion. In EXP, optional biopsies include pre-treatment, during treatment, and one or more at times of suspected and/or confirmed progression.

¹⁰ To be performed at end of odd-numbered cycles (Cycle 3, 6, 9, etc.) prior to start of the next treatment cycle. RECIST 1.1 (APPENDIX K) measurements for patients with solid tumors; IWG 2014 (APPENDIX L) measurements for patients with lymphoma. In DEP, after 1 year, assessments will be obtained at approximately 3 month intervals. After 2 years, assessments will be obtained at approximately 4 month intervals or per standard of care. In EXP, the frequency of imaging will not change after 1 year of treatment.

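### In Appendices E and F the DR-B expansion biopsy day (Day 3 or 10) conflicts with its own footnote (48 hours around the Day 11 infusion), so on-treatment samples taken at different points after dosing may be pooled

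*Protocol*

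**What the plan says.** The DR-B expansion schedule in the Protocol synopsis is "Dose Regimen B 2.7 mg/kg on Days 1 and 4, 8 and 11 in a 21-day cycle (1 hour infusion").

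In Appendix E (DR-B, Cycle 1), the row for the biomarker and p53 biopsy reads Day 3 or 10 for the expansion, and the cell is tagged to footnote 1. That footnote, for patients who had a study biopsy immediately before enrollment, reads: "optional needle biopsy to be performed within 24 (DEP) or 48 (EXP) hours of Cycle 1 Day 11 infusion OR Cycle 2 Day 11 infusion". Appendix F (DR-B, Cycle 2 onward) has the same Day 3 or 10 cell, tagged to footnote 9, which again says "within 24 hours (DEP) or 48 hours (EXP) of Cycle 1 Day 11 infusion OR Cycle 2 Day 11 infusion".

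The Day 3 entry has support elsewhere. Appendix E footnote 9 keeps that day's visit for the expansion: "Visit to be completed in EXP only if biopsy performed". Appendix F has an expansion-only Day 3 column. The Day 12 column, which would suit a sample taken after the Day 11 dose, is restricted to dose escalation in both appendices.

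On analysis, Section 7.5 defines the material as "tumor specimens collected before beginning treatment, during Cycle 1 or Cycle 2 and at suspected disease progression". It summarizes pharmacodynamic data for each patient and collectively by dose level. The SAP (Section 3.1) covers Phase 1 only and leaves Phase 2a and pharmacodynamics to separate plans.

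**The concern.** A site cannot follow both instructions. One that reads the table may sample two days after the first infusion. One that reads the footnote may sample after the fourth. Section 7.5 gives both samples the same description and does not separate them by biopsy day, hours since dosing or number of infusions received.

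The effect of treatment on tumor biomarkers such as p53, p21, caspase, MDM2 and MDMX, and its possible correlation with clinical outcome, is a Phase 2a secondary objective (Section 2.2.2). The PTCL endpoints include "p21 RNA and/or protein expression) in tumor biopsy samples". Each expansion cohort is planned at about 15 to 25 patients (Section 3.3) and the biopsies are optional, so pairs may be few. In a small set, a change in an expression marker could be blurred, or an apparent one produced, by differences in when the samples were taken.

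**Working it through.** The documents give no sample size or error rate on this point, so the check is a count of days.

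**Inputs.** Infusion days 1, 4, 8 and 11 of a 21-day cycle at 2.7 mg/kg (synopsis). Table biopsy days 3 and 10 (Appendices E and F). Footnote window of 48 hours relative to Day 11 (Appendix E footnote 1, Appendix F footnote 9).

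**Can the table days satisfy the footnote?**

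- Day 3 to Day 11: (11 − 3) × 24 = 192 hours. This is outside 48 hours in either direction.
- Cycle 2 Day 3 is study day 21 + 3 = 24. From Cycle 1 Day 11 that is (24 − 11) × 24 = 312 hours, so the Cycle 1 infusion does not rescue it either.
- Day 10 to Day 11: (11 − 10) × 24 = 24 hours before the dose. This fits only if the window is two-sided (Days 9 to 13).

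**Infusions received before each biopsy point** (nominal days, no dose missed; Cycle 2 adds the 4 infusions of Cycle 1):

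| Biopsy point | Source | Hours since last infusion | Infusions, Cycle 1 | Cumulative, Cycle 2 |
|---|---|---|---|---|
| Day 3 | Table | (3 − 1) × 24 = 48 | 1 | 4 + 1 = 5 |
| Day 10 | Table; footnote if two-sided | (10 − 8) × 24 = 48 | 3 | 4 + 3 = 7 |
| After Day 11, up to Day 13 | Footnote | up to (13 − 11) × 24 = 48 | 4 | 4 + 4 = 8 |

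Under the two-sided reading, Day 9 and Day 11 before the dose also follow 3 infusions, so the set of counts does not change.

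**Cumulative nominal dose.** In Cycle 1 the range is 1 × 2.7 = 2.7 to 4 × 2.7 = 10.8 mg/kg. Over both cycles the table alone spans 2.7 to 7 × 2.7 = 18.9 mg/kg, and the footnote extends this to 8 × 2.7 = 21.6 mg/kg.

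**Sensitivity to visit windows.** In Cycle 1 the expansion allows a day either way on dosing days ("Days 4 and 8 EXP: ± 1 d", and the same for Day 11). If the Day 11 infusion is given on Day 10, Day 3 is still (10 − 3) × 24 = 168 hours away. If the Day 4 dose is given on Day 3, or the Day 11 dose on Day 10, and the biopsy follows it the same day, the count becomes 2 or 4. If the Day 8 dose moves to Day 9 or Day 7, a Day 10 biopsy falls 24 or 72 hours after it. Nominal day is therefore an imperfect label even once the text is reconciled.

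**The case against.** Much of the case on the other side stands.

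- **Pooling is not shown.** The biopsies are optional. Sections 3.2.1 and 6.3 send the reader to the Laboratory Manual, and the pharmacodynamic and Phase 2a analyses have their own plans. Any of these could fix the timing or stratify by it. None is among the documents, so pooling is a risk, not an outcome.
- **Most of the spread comes from the table.** The table alone permits 1, 3, 5 or 7 infusions. The footnote adds 4 and 8. Other regimens also offer alternatives: DR-A allows Cycle 1 or Cycle 2 Day 15, and DR-C allows a biopsy after the Day 1 or Day 3 infusion. Some variation in cumulative dose is a permitted choice.
- **Only Day 3 is irreconcilable.** Day 10 fits a two-sided window.
- **The missing visit cuts both ways.** Day 13 has no column, but neither does Day 10, and the footnote window includes Day 11, which has one.
- **Not every marker need be time-sensitive.** The endpoint also covers gene sequence and copy number, and the biopsy row also serves p53 status. Nothing in the documents suggests that these vary with hours since dosing as expression markers may.

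None of this removes the contradiction between a cell and the footnote attached to it, and no document supplied resolves it. Day 3 and Day 10 are each 48 hours after an infusion, so the footnote may simply name infusions that were not updated. That is inference and does not tell a site what to do.

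**Conclusion.** The contradiction is real and sits in the operative text of both appendices. Its consequence is a risk to a secondary, descriptive analysis: samples taken after 1, 3 or 4 infusions in Cycle 1, or 5, 7 or 8 cumulatively in Cycle 2, could be summarized under the single description "during Cycle 1 or Cycle 2 and at suspected disease progression". These counts assume nominal days and no missed doses. The number of biopsies involved cannot be stated from the documents. No primary endpoint, sample size or error rate is touched, and the point is minor.

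Four stronger readings are tempting but unsupported:

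- *Every DR-B expansion biopsy is affected.* If all sites followed the table, the conflict itself would affect none.
- *The problem is exclusive to DR-B.* In Appendix D the DR-A biopsy sits in a Day 16 column with a two-day window either side, while its footnote requires sampling within 24 hours of the Day 15 infusion. That fit is also loose, though it is not a direct contradiction.
- *A comparison of DR-B with DR-A or DR-C is confounded.* No such pharmacodynamic comparison is specified. Section 7.1 makes the analyses descriptive.
- *Some biopsies should leave a main paired comparison.* The documents define no such comparison.

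**What to change.** Reconcile the DR-B biopsy cells and footnotes in Appendices E and F so that each pair names the same infusion or infusions, states whether the window lies before or after the infusion, and matches a visit in the schedule. Which day or days to keep is for the sponsor to decide. More than one may remain if the text is consistent.

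In Section 7.5 and the pharmacodynamic analysis plan, classify each on-treatment biopsy by actual hours since the most recent ALRN-6924 infusion and by number of prior infusions. Present the time- and dose-sensitive expression markers by that classification. Gene sequence and copy number need not be split this way.

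The cost is wording in two appendices and one section, which can go into the next amendment, plus two derived variables in a plan that the SAP says is still to be developed. It needs biopsy and infusion dates and times on record. No extra biopsy is required and no sample is discarded.
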